3.1 Inclusion

1. Patients must have histologically confirmed newly diagnosed or previously untreated (patients may be under no treatment “wait and watch” or have received two cycles of chemotherapy or localized radiation therapy before informed consent) Non-Hodgkin’s Lymphoma or CLL.
2. Patients must be 18 years of age or older (19 years or older in Nebraska).
3. Patients must have serum 25-hydroxyvitamin D [25(OH) D] drawn at time of enrollment. (NOTE: subjects currently taking Vitamin D supplements are eligible for screening. See Exclusion 2.)
4. Simultaneous participation in other therapeutic clinical trials will be allowed.
5. Patients must be aware of the neoplastic nature of his/her disease and willingly provide written, informed consent after being informed of the procedure to be followed, the nature of the therapy, alternatives, potential benefits, side-effects, risks, and discomforts.

3.2 Exclusion

1. History of uncontrollable allergic reactions to vitamin D
2. Currently taking vitamin D supplement ≥ 1000 IU/day
3. History of Paget’s disease.
4. Hypercalcemia
5. Any other clinically significant medical disease or condition laboratory abnormality or psychiatric illness that, in the Investigator’s opinion, may interfere with protocol adherence or a subject’s ability to give informed consent.
6. Inability to cooperate with the requirements of the protocol.

Section 4.0: Registration and Randomization Procedures:

4.1 Recruitment

Patients with newly diagnosed or previously untreated (patients may be under no treatment “wait and watch” OR have received two cycles of chemotherapy before informed consent) Non-Hodgkin’s Lymphoma or CLL may be eligible for this trial.

Screening eligibility based on standard clinical care will be performed by the treating physician at the time of encounter. On initial presentation, a history and physical examination are performed, laboratory data obtained, radiologic/imaging, or bone marrow evaluations for staging will be performed per standard practice and as clinically indicated and is at the discretion of the treating physician.

The patient's primary oncologist will make the decision as to screened eligibility of the candidate based on the eligibility criteria listed in Section 3.0 prior to offering consent.

If the patient is screened as potentially eligible, he/she will then be offered the option to participate. An informed consent will be signed by the patient after thorough review of the study is completed by the physician and his/her designee.

Some insurance carriers may decline to cover the costs of usual medical care if the patient is participating in a clinical trial. The patient will be provided assistance by the research nurse coordinator or designated staff in determining if the insurance carrier will decline coverage. Insurance carriers may or may not pay for study related expenses. The patient can then decide if they wish to participate.

4.2 Eligibility Verification/Registration:

Before subjects are registered to the study, the Eligibility Checklist (Appendix A) must be completed to verify the subject meets the eligibility criteria. This will be used as source documentation once it has been reviewed, signed, and dated, which should be done prior to registration by the treating physician.

Date of Enrollment: The date of consent will be considered the date of enrollment.

Subjects will be registered through the sponsor site (UNMC) by contacting the UNMC Project Coordinator. Study personnel from UNMC, affiliate and IRB approved non-UNMC sites will contact the UNMC Project Coordinator if a potential subject appears to meet the eligibility criteria.

The site will email the following information:

- Registration request (which includes the subject's demographics)
- Completed Eligibility Checklist (Appendix A), and
- Signed consent form.

Once the UNMC Research Project Coordinator confirms that all documents have been received, approval for the patient will be given with an assigned study subject number. The UNMC IIT Project Coordinator will send a confirmation of registration email to the site. (Please note: A Study Subject ID number can be assigned prior to final confirmation, if needed.)

Each subject consented to the protocol is loaded into the UNMC Clinical Trial Management System (CTMS) within one week of consent. CTMS registration includes entering the required demographic information (included on the registration request form) as stated in the SRC policies and procedures. For external sites, this is completed by the UNMC Research Project Coordinator.

Section 5.0 Treatment Plan:

This is a Pilot study evaluating the effects of vitamin D supplementation on the outcomes of patients with newly diagnosed or previously untreated (patients may be under no treatment "wait

and watch” OR have received two cycles of chemotherapy or localized radiation therapy before informed consent) Non-Hodgkin’s Lymphoma or CLL.

5.1 Randomization plan

This is a randomized study. All subjects will have a serum 25-hydroxyvitamin D [25(OH) D] drawn at time of enrollment. (NOTE: Only subjects currently taking < 1000 IU Vitamin D supplements are eligible for screening.) Subjects found to have **low levels** of serum 25-hydroxyvitamin D [25(OH) D] <30 ng/ml will be randomized on a 1:1 basis to vitamin D 5000 IU daily (Higher Dose Cohort) or vitamin D 1000 IU daily (Lower Dose Cohort) and stratified by disease group (aggressive NHL or indolent NHL/CLL).

The randomization schedule is generated by the study statistician. The randomization schedule is then provided to the UNMC research pharmacist.

Site study personnel will complete the Subject Randomization Request for those subjects meeting criteria for randomization and submit this along with the registration request documents outlined in Section 4.2 to the UNMC project coordinator. The UNMC research pharmacist will assign a randomization number and cohort. When finalizing the registration procedures, the randomization assignment is sent to study personnel by the UNMC project coordinator.

5.2 Evaluations

Pre-treatment Evaluations Within One Month (30 Days) of Consent:

- History and physical
- Calcium level
- Serum 25-hydroxyvitamin D [25(OH) D]
- Height and weight
- Vital signs, including blood pressure

If subjects have a **normal level** of serum 25-hydroxyvitamin D [25(OH) D] ≥ 30 ng/ml at time of enrollment, the subject will automatically be enrolled in the controlled group and will be followed only for long-term progression free survival and outcome. No further evaluation of serum 25-hydroxyvitamin D [25(OH) D] will be obtained. (NOTE: Subjects currently taking Vitamin D supplements will be encouraged to continue their supplementation.)

If subjects are found to have **low levels** of serum 25-hydroxyvitamin D [25(OH) D] <30 ng/ml at time of enrollment, the subjects will be randomized to receive either vitamin D 5000 IU (5 tablets) daily (Higher Dose Cohort) or vitamin D 1000 IU (one tablet) daily (Lower Dose Cohort) for three years. To provide a means of ensuring oral routes of medication adherence of patients while participating in a clinical trial, **Appendix D** “Oral, Sublingual, and/or Buccal Route Medication Adherence Standard Procedure (V 1.0 11-25-2013)” will be followed. (NOTE: Subjects who were currently taking Vitamin D supplements at the time of screening will be asked to discontinue the use of their Vitamin D supplementation and use only the Vitamin D dosing and supply instructed by the study.)

UNMC subjects will take oral over the counter supply through UNMC pharmacy.

Subjects at affiliate and Non-UNMC IRB approved sites will take oral over the counter Vitamin D 1000 IU (vitamin D-3, (cholecalciferol)) tablets. Investigators will need to prescribe the appropriate dose in which the subject is randomized.

Follow-up Evaluations

Subjects randomized to the Vitamin D cohorts: at 6 months, 12 months, and year 2 and 3 (Day 1095) (+/- 30 days) from registration confirmation:

- Serum 25-hydroxyvitamin D [25(OH) D] (Levels will be measured at a location convenient for the patient, for example, at their local primary care provider office.)

After year 3 (1095 days), the investigator will discuss continuation of Vitamin D supplementation recommendations with the subject. The supply of any recommendations for continued Vitamin D will be at the subjects cost.

Control group subjects: disease status must be assessed at the end of 3 years. Three years is defined as from the time of registration confirmation to day 1095 (+/- 180 days). For subjects no longer being followed by the study site, an attempt should be made by contacting the referring physician or reaching out to the subject at the 3-year time point to assess survival or progression free survival status. Contact and subject status should be documented in the medical record.

Covid Visit Exceptions:

If a subject visit is cancelled due to Covid concerns, then the study staff will confirm with the subject that they have an adequate supply of the study vitamin D supplement to continue daily dosing as prescribed.

The lab work required for the study will be collected at their next visit.

The Vitamin D administration diary may be collected at their next visit or via US Mail.

The visit will be documented as delayed due to Covid. The visit schedule will otherwise be maintained so that subject is on study for 3 years per protocol. The above will be fully documented in the medical record.

Dose Modifications based on vitamin D levels at 6 month, 12 month and year 2 and 3.

If subject is at a **normal level** (30-100 ng/ml) of 25-hydroxyvitamin D [25(OH) D], no change in intervention will be made.

If the subject has a **low level** of 25-hydroxyvitamin D [25(OH) D], which is defined as [OH] D < 30 ng/ml, then the dose that they are currently enrolled in will be increased 1000 IU (e.g. 5000

IU increase to 6000 IU; 1000 IU increase to 2000 IU). There will be a maximum dose of 10000 IU daily.

If a subject has an **elevated level** of 25-hydroxyvitamin D [25(OH) D], which is defined as [OH] D > 100 ng/ml, then the dose will be held for one month and a level will be rechecked. If the repeat level is < 100 mg/ml, the dose will be cut in half and re-tested in two months.

After the 12 month time point, if Vitamin D levels are not within normal limits, the investigator may manage subjects as clinically indicated, i.e. levels can be monitored more frequently than annually. Dose adjustment will be managed according to guidelines above or as recommended by the patient's primary care physician or Endocrinologist.

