6.2 Survival

Subjects will be analyzed with respect to overall and progression-free survival.

Overall survival is defined as time from study entry until death from any cause. For subjects who are still alive at the time of the study analysis or are lost to follow-up, survival will be censored at the last recorded date that the subject was known to be alive.

Progression-free survival is defined as time from study entry until the first notation of clinical progression, relapse, starting new therapies or death from any cause. For subjects who are still progression-free at the time of the study analysis or are lost to follow-up, progression-free will be censored at the last recorded date that the subject was known to be progression-free.

Response will be determined by the Principal Investigator or the lead site investigators.

Section 7.0 Study Parameters:

	Low Levels <30 ng/mL - RANDOMIZED GROUP					
	Pre-Treatment (within 30 days of Consent)	First Dose	6 months Day 182 (+/- 30 Days)	12 months Day 365 (+/- 30 Days)	Year 2 Day 730 (+/- 30 Days)	Year 3 Day 1095 (+/- 30 Days) End of Study
History & Physical	X					
Height, Weight, Vital Signs	X					
Monitor for Vitamin D related AEs			X	X	X	X
Serum Calcium	X					
Serum 25- hydroxyvitamin D [25(OH) D]	X		X	X	X	X
Vitamin D		X - Daily Dosing at Home for 3 years				
Long-term progression free survival and outcome ¹						X

Normal Level $\geq 30\text{ng/ml}$ - CONTROL GROUP*		
Followed only for long-term progression free survival and outcome. No further evaluation of serum 25-hydroxyvitamin D [25(OH) D] will be obtained. (NOTE: subjects currently taking Vitamin D supplements will be encouraged to continue their supplementation.)		
Required studies	Pre-Treatment (Within 30 days of Consent)	Year 3 - Day 1095 (+/- 180 Days) End of Study
History & Physical	X	
Height, Weight, Vital Signs	X	
Serum Calcium	X	
Serum 25-hydroxyvitamin D [25(OH) D]	X	
Long-term progression free survival and outcome ¹		X

¹ Progression defined as relapse, progression, or starting new therapies, or death

Section 8.0 Drug Formulation and Procurement (per UNMC Lexicomp Online):

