8.1.7 Toxicology

Toxicity due to vitamin D is considered to manifest at serum levels greater than 150 ng/mL of 25-hydroxyvitamin D. Symptoms of hypervitaminosis D include fatigue, nausea, vomiting, and weakness associated with hypercalcemia. (Page 27 sites more toxicity details)

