12.10 Potential Risks

A rare but potential harm of treatment with oral vitamin D is toxicity, which may lead to hypercalcemia, hyperphosphatemia, suppressed parathyroid hormone, and hypercalciuria. However, the 25-(OH) D level associated with toxicity (often defined as >500 nmol/L [>200 ng/mL]) is well above the level considered to be sufficient. Treatment with vitamin D plus calcium may also be associated with increased risk for kidney stones; vitamin D alone does not seem to increase this risk. It is believed the treatment option outlined in the study will not pose significant additional risks compared to conventional treatment.

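### Serum calcium is required only before treatment, so asymptomatic hypercalcemia during three years of vitamin D is found only if routine care happens to measure it

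*Combined protocol and SAP*

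**What the plan says.** Section 5.2 places the calcium level in the list headed "Pre-treatment Evaluations Within One Month (30 Days) of Consent". For the randomized arms it then sets follow-up "at 6 months, 12 months, and year 2 and 3 (Day 1095) (+/- 30 days) from registration confirmation", with 25(OH)D as the only item. The draw may be done elsewhere: "Levels will be measured at a location convenient for the patient, for example, at their local primary care provider office".

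The Section 7.0 table agrees. Serum calcium and the history and physical are each marked once, in the pre-treatment column. The row "Monitor for Vitamin D related AEs" is marked at 6 months, 12 months, year 2 and year 3, with no test attached to it. Section 9.0 names patient reports, standard laboratory results and physical examinations as the sources of adverse events. Section 6.1 limits assessment to related grade 3 and 4 toxicities.

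The dose rules in Section 5.2 depend on 25(OH)D alone. Below 30 ng/mL the dose rises by 1000 IU, up to 10000 IU daily. Above 100 ng/mL it is held for one month and the level rechecked; once the level is below 100 the dose is halved, with a retest two months later.

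On calcium as a hazard, the exclusions in Section 3.2 include "4. Hypercalcemia". Section 12.10 describes the potential harm as "toxicity, which may lead to hypercalcemia, hyperphosphatemia, suppressed parathyroid hormone, and hypercalciuria". Section 8.1.7 adds: "Symptoms of hypervitaminosis D include fatigue, nausea, vomiting, and weakness associated with hypercalcemia".

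**The concern.** The protocol treats calcium as a safety matter at entry and in its risk statement, then requires no further value while patients take vitamin D for three years. A patient whose calcium rises without symptoms could continue dosing, because the only laboratory result with a stated action is 25(OH)D.

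Symptoms are a weak substitute. Those listed in Section 8.1.7 are non-specific, and Section 2.0 gives fatigue as a symptom of lymphoma. Without a calcium value it is hard to attribute them to vitamin D.

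The second consequence concerns reporting. If calcium is measured only when routine care calls for it, the number of patients examined is unknown. A statement that no hypercalcemia was seen could then reflect either no cases or little testing.

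**Working it through.** The plan gives no hypercalcemia rate and no figure on this point to reproduce. The check is a reading of the schedule, followed by an illustration.

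**What can detect raised calcium after baseline**

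| Route | Where | Measures calcium? |
|---|---|---|
| 25(OH)D at 6, 12, 24 and 36 months | 5.2, 7.0 | No |
| Adverse event check at the same visits | 7.0 | No test attached |
| Physical examination | Named in 9.0; scheduled only at baseline in 7.0 | No |
| Standard laboratory results | Named in 9.0; no calcium test required after baseline | Only if routine care orders it |

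The gaps between 25(OH)D draws are 6, 6, 12 and 12 months. Because of the restriction to grade 3 and 4 related events, milder hypercalcemia would not be counted even if routine care found it.

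**Dose reached.** Scheduled steps from 5000 IU, taken only if 25(OH)D stays low, are 6000 (month 6), 7000 (month 12) and 8000 IU (year 2); year 3 ends dosing. This is not the protocol's maximum. After month 12, Section 5.2 allows more frequent levels and adjustment by the primary care physician or endocrinologist, and the cap is 10000 IU.

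**What a zero count would support.** Inputs: 70 patients per arm (Section 10.1). The numbers tested in routine care (35 or 18) and the true risks below are assumptions. Tested patients are taken as a random subset of the arm, and a case is taken to show at a draw.

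With zero cases in n tested, the one-sided 95% upper limit U solves (1 − U)^n = 0.05, so U = 1 − 0.05^(1/n).

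- n = 70: U = 0.0419, or 4.2%
- n = 63 (70 × 0.9, applying the roughly 10% loss in Section 10.1): U = 0.0464, or 4.6%
- n = 35: U = 0.0820, or 8.2%
- n = 18: U = 0.1533, or 15.3%

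The chance of seeing at least one case is 1 − (1 − q)^n for a true three-year risk q:

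| q | 70 tested | 35 tested | 18 tested |
|---|---|---|---|
| 1% | 0.505 | 0.297 | 0.165 |
| 2% | 0.757 | 0.507 | 0.305 |
| 5% | 0.972 | 0.834 | 0.603 |

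**Cost of testing.** 4 draws × 140 randomized patients = 560 tests at most, before rechecks.

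**The case against.** The strongest defense is that 25(OH)D is a reasoned trigger. Sections 8.1.7 and 8.5 place toxicity above 150 ng/mL, and Section 2.6 reports no intoxication below 200 ng/mL or below 30,000 IU daily. Holding the dose above 100 ng/mL therefore acts before the levels at which the protocol expects harm. The agent is sold over the counter, Section 12.10 calls toxicity rare, and adverse events are checked at four visits. Section 5.3 removes a patient when continuing would be detrimental, and Section 9.1.1 can make a laboratory abnormality an adverse event.

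Most of this stands, and it keeps the point minor. Three limits remain. The 25(OH)D result does not measure calcium, and draws are 6 to 12 months apart. The provisions in Sections 5.3 and 9.1.1 act once raised calcium is known; they do not find it. The cited absence of hypercalcemia at up to 50,000 IU daily covers 1 to 5 months, against three years here.

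The illustration is also open to challenge. If routine care tests mainly patients with symptoms, the random-subset assumption overstates the loss of detection. It would still leave asymptomatic cases unseen.

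Two stronger readings are tempting, and the documents support neither.

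- A reader might infer that calcium testing differs between arms, since the dose is known: "Investigators will need to prescribe the appropriate dose in which the subject is randomized". Knowledge of the dose makes this possible, but nothing in the documents shows that testing differs.
- A reader might infer that the 10% safety stopping rule in Section 10.4.1 is compromised. That rule concerns severe related events and needs 7 of 70 patients. At true risks of 1% to 5% it is reached at most 6% of the time even if every event is found (P(Bin(70, 0.05) ≥ 7) = 0.060). Most values just above a laboratory limit need not be severe.

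**Conclusion.** The point holds as a minor patient-safety improvement. It is plain from Sections 5.2 and 7.0 that no calcium test is required after baseline and that no calcium result has a stated action. Asymptomatic hypercalcemia therefore comes to light only through testing outside the protocol.

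The expected risk looks low on the protocol's own evidence, and existing 25(OH)D monitoring gives indirect protection. The gain is in finding individual patients and in a safety statement with a known denominator: an upper limit of 4.2% rather than, for example, 8.2% after zero cases. Those figures depend on assumed numbers tested and a random subset. Sample size, alpha, power and the primary analysis are unaffected.

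**What to change.** In Sections 5.2 and 7.0, add serum calcium to the 25(OH)D draws at 6, 12, 24 and 36 months and to the one-month recheck after a level above 100 ng/mL. Add this rule:

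- Calcium above the local laboratory's upper limit: hold vitamin D and repeat calcium in one month.
- Normal on repeat: resume at half dose, or at full dose if another cause has been identified.
- Still high on repeat: stop vitamin D and evaluate.

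State that this rule takes precedence over the 1000 IU increase for low 25(OH)D. At 36 months, where study dosing ends, the result informs the discussion of continued supplementation. Report by arm the number tested and the number above the limit.

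The cost is one amendment and at most 560 scheduled tests plus rechecks, using draws that already take place. Local offices must add calcium to the order, some mild results will need follow-up, and some patients will miss vitamin D for a rise with another cause. If enrollment is complete, test at the remaining visits and collect calcium values already in the charts, marked as routine-care values.

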Subjects with a **normal level** of serum Vitamin D 30-100 ng/ml at time of enrollment will be automatically enrolled in the controlled group and will be followed only for long-term progression free survival and outcome. No further evaluation of serum 25-hydroxyvitamin D [25(OH) D] will be obtained.

Subjects found to have **low levels** of serum Vitamin D <30 ng/ml at time of enrollment will be randomized on a 1:1 basis to receive vitamin D 5000 IU daily (Higher Dose Cohort) or vitamin D 1000 IU daily (Lower Dose Cohort) stratified by disease group (aggressive NHL or indolent NHL/CLL).

Evaluation: Serum 25-hydroxyvitamin D levels will be assessed at baseline, 6 months from baseline, 12 months from baseline, and then year 2 and 3. If subject is at a normal level of 25-hydroxyvitamin D [25(OH) D], no change in intervention will be made. If the subject has a low level of vitamin D, which is defined as < 30 ng/ml, then the dose that they are currently enrolled in will be increased by 1000 IU (e.g. 5000 IU increase to 6000 IU; 1000 IU increase to 2000 IU). There will be a maximum dose of 10000 IU daily. If a subject has an elevated level of vitamin D, which is defined as > 100 ng/ml, then the dose will be held for one month and the level will be rechecked. If the level returns < 100 mg/ml, the dose will be cut in half and re-tested in two months. PFS and OS will be assessed at the end of study (3 years).

Schema:

**A Pilot Study of Vitamin D Replacement in Patients with
Non-Hodgkin's Lymphoma and Chronic Lymphocytic Leukemia
With Low Vitamin D Levels**

[figure not shown]

Table of Contents

Abstract	Page 2
Schema	Page 3
Section 1.0 Objectives	Page 5
Section 2.0 Background	Page 5
Section 3.0 Eligibility Criteria	Page 11
Section 4.0 Registration/Randomization Procedures	Page 11
Section 5.0 Treatment Plan	Page 13
Section 6.0 Measurement of Effect	Page 15
Section 7.0 Study Parameters	Page 17
Section 8.0 Drug Formulation and Procurement	Page 18
Section 9.0 Toxicity Reporting Guidelines	Page 28
Section 10.0 Statistical Considerations	Page 31
Section 11.0 Records to Be Kept	Page 34
Section 12.0 Patient Consent Form Statement	Page 34
Section 13.0 References	Page 36
Section 14.0 Data Forms	Page 38
Appendix A Eligibility checklist	Page 39
Appendix B NCI Common Toxicity Criteria Version 4.0 (CTCAE)	Page 41
Appendix C FDA MEDWATCH form	Page 41
Appendix D Oral, Sublingual, and/or Buccal Route Medication Adherence Standard Procedure (V 1.0 11-25-2013)	Page 42

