5.5 Patient chooses to discontinue treatment or follow-up

In this event, the reason(s) for withdrawal will be documented.

The reason(s) for withdrawing the patient from the treatment portion of the study will be documented in the case report form. If available, the following information will be recorded in the case report form: date of disease relapse, date of death, cause of death, and autopsy report.

Section 6.0 Measurement of Effect:

To avoid assay variability which can confound vitamin D determinations a radioimmunoassay method will be used to measure all vitamin D measurements by liquid chromatography-tandem mass spectrometry (LC-MS/MS) (this is the Nebraska Medicine's standard). Calibration used a 6-point standard curve over a concentration range 0-100 ng/mL. This is the preferred test for assessment of vitamin D is serum 25-hydroxyvitamin D (25(OH) D). The reason for this test is because it is minimally influenced by recent dietary intake or recent sun exposure, and it is considered the most accurate functional indicator of vitamin D stores. However, if this method is not available, the method used by the local lab will be acceptable.

Study ranges used:

- <30 is considered inadequate
- 30-80 Adequate

- >150 Potentially toxic vitamin D level

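### The recheck threshold for restarting vitamin D after a hold is printed in mg/ml instead of ng/ml, in both places where the rule can be read

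*Combined protocol and SAP*

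**What the plan says.** The hold-and-recheck rule can be read in two places in the combined protocol and SAP (Version 6.4).

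- **Abstract, Evaluation.** An elevated level is one "which is defined as > 100 ng/ml, then the dose will be held for one month and the level will be rechecked". The restart condition is then: "If the level returns < 100 mg/ml, the dose will be cut in half and re-tested in two months".
- **Section 5.2, Dose Modifications.** An elevated level is one "which is defined as [OH] D > 100 ng/ml, then the dose will be held for one month and a level will be rechecked". The restart condition is then: "If the repeat level is < 100 mg/ml, the dose will be cut in half and re-tested in two months".

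Section 5.2 sets the normal range, in which the dose is left alone, at 30 to 100 ng/ml. Section 6.0 (Measurement of Effect) says of the assay: "Calibration used a 6-point standard curve over a concentration range 0-100 ng/mL". Its list of study ranges ends with ">150 Potentially toxic vitamin D level"; that entry carries no unit, but Section 8.1.7 gives the same 150 figure in ng/mL.

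**The concern.** The trigger and the restart threshold belong to one rule and should be on one scale. As printed, the dose stops on a value in ng/ml and restarts on a value in mg/ml. The recheck is the step that decides whether a held patient resumes dosing, and a threshold that no serum level can reach removes that decision.

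The wording matters because the rule is an instruction that several parties apply. Section 5.2 lets levels be drawn at a site convenient to the patient, such as a primary care office, and has investigators at affiliate sites prescribe the dose. Section 6.0 accepts a local laboratory's own method. In the Section 7.0 schedule, serum calcium appears only before treatment, so 25(OH)D is the only laboratory test scheduled during dosing. Section 6.1 limits toxicity assessment to grade 3 and 4 events related to vitamin D.

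**Working it through.** **Unit check**

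| Item | Printed value | Source |
|---|---|---|
| Hold trigger | > 100 ng/ml | Abstract; Section 5.2 |
| Normal range | 30 to 100 ng/ml | Abstract; Section 5.2 |
| Restart threshold | < 100 mg/ml | Abstract; Section 5.2 |
| Assay calibration | 0 to 100 ng/mL | Section 6.0 |
| Toxicity level | > 150 ng/mL | Section 8.1.7 |

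1. Conversion: 1 mg = 10^6 ng, so 100 mg/ml = 100 × 10^6 = 10^8 ng/ml.
2. Relative to the hold trigger: 10^8 / 100 = 10^6.
3. Relative to the toxicity level: 10^8 / 150 ≈ 667,000.
4. Literal consequence: 100 mg/ml is 100 g per litre of serum. No 25(OH)D value can approach that, so every recheck satisfies the restart condition.
5. With ng/ml in its place, the restart threshold (< 100 ng/ml) meets the hold trigger (> 100 ng/ml) and the top of the normal range, and the rule is coherent.

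**How far a typical patient is from the hold trigger**

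Section 2.5 gives an expected rise of 1 ng/ml for each additional 100 IU/day. This assumes full adherence and no earlier supplement; a patient who stops their own supplement of under 1000 IU/day would have a net rise up to 10 ng/ml smaller.

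- 5000 IU: 5000 / 100 = +50, so a patient starting below 30 is expected to stay below 80 ng/ml.
- 1000 IU: 1000 / 100 = +10, so the same patient is expected to stay below 40 ng/ml.
- To pass 100 from a baseline of 30, the rise must exceed 70, which is 70/50 = 1.4 times the expected rise on 5000 IU, or 70/10 = 7 times on 1000 IU.
- From a baseline of 20, the rise must exceed 80, which is 80/50 = 1.6 times or 80/10 = 8 times.

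These figures place the average patient below the trigger in both arms. They do not give the share of patients who would be held, because the documents state no between-patient spread.

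**The case against.** The strongest reply is that this is a proofreading slip that cannot change conduct. In both places the preceding sentence sets the trigger in ng/ml, the Abstract speaks of the level returning below 100, and 100 mg/ml is physically impossible in serum. The factor of 10^6 then measures the size of the typing error, not an effect on the trial. This largely stands, and it is why the point ranks low.

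A second reply is that patients are protected even under the literal text. The dose is still held for a month, halved and re-tested. Section 5.2 adds discretion later: "After the 12 month time point, if Vitamin D levels are not within normal limits, the investigator may manage subjects as clinically indicated". Section 5.3 allows removal from therapy when the protocol is detrimental to the patient, and Section 7.0 schedules monitoring for vitamin D related adverse events at every follow-up visit. Section 2.6 reports no intoxication below 200 ng/ml, and Section 12.10 also puts toxicity above 200 ng/mL, so 150 is the more cautious of the document's two figures. This stands too.

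A third reply is that holds cannot be called uncommon on the strength of an average rise alone. That is right. On 5000 IU the margin is only 1.4 to 1.6 times the expected rise, and without a spread no frequency follows. Few holds is a reasonable expectation, but it is an assumption.

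None of this makes the printed threshold correct. An obvious intention lowers the severity of an error in a dosing rule; it does not remove the error.

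**Conclusion.** The point holds. Both readable statements of the restart threshold carry the wrong unit, by a factor of 10^6, and taken literally the recheck excludes no one. The schema figure and one passage missing from the review copy could not be checked.

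The grade is a minor correction to a safety rule. Practical risk is low because the intended unit is unmistakable from the adjacent text and the rest of the rule limits exposure. That judgement does not depend on how often holds occur. No sample-size, power or alpha figure and no planned analysis changes.

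**What to change.** Replace mg/ml with ng/ml in the restart condition, once in the Abstract and once under Dose Modifications in Section 5.2. Check the schema figure for the same slip while doing so.

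As an optional clarification, add a sentence stating that a recheck still at or above 100 ng/ml continues the hold, with monthly rechecks. That is the natural reading of the elevated-level rule, but it is not written down. It matters mainly for a hold begun at month 6, because explicit clinical discretion starts only after month 12.

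The cost is two unit corrections, and at most one added sentence, at the next amendment.
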